I will share the protocol and all other important study-related information with the staff and investigators participating in the study so that they can conduct the study correctly. I am aware of my responsibility to keep staff and investigators working on the study informed and trained on an ongoing basis.

I am aware that quality control will be carried out on the study in the form of monitoring, auditing, and possible inspection.

Principal investigator's signature

Date

Name

Synopsis

Protocol title	Immunological response after vaccination with the mRNA vaccine against COVID-19, Comirnaty, in immunosuppressed and immunocompetent individuals – an open-label, non-randomised, multicentre Phase IV study
English abbreviation of title	COVID-19 vaccination of immunodeficient persons (COVAXID)
EudraCT No	2021-000175-37
Medicinal	Comirnaty
Development phase	Phase IV
Indication	Active immunization to prevent COVID-19 caused by the SARS-CoV-2 virus

Design	Phase 4, open-label, non-randomized cohort study. The Comirnaty vaccine will be administered in two doses. Blood and saliva analyses will be performed to assess humoral and cellular responses. The occurrence of local or systemic reactogenicity, as well as AE/SAE/SUSAR, will be evaluated.
---------------	--

Background Objective	Comirnaty is an mRNA-based vaccine approved since December 2020, indicated for active immunization to prevent COVID-19 caused by the SARS-CoV-2 virus. The vaccine has been shown to be highly effective in clinical trials, but people with immunosuppressive diseases or immunosuppressive treatment were excluded from these trials. However, these individuals are at risk of serious complications, including increased mortality from COVID-19. There is currently a knowledge gap regarding how immunosuppressed patients, whether primary or secondary, respond immunologically to mRNA vaccines, including the current vaccine, and whether they extended protection against severe COVID-19. It is also unclear at present whether they react differently than healthy individuals in terms of side effects.
-----------------------------	--

Primary objective: to investigate the immunological effect of Comirnaty by measuring the incidence of seroconversion (development of antibodies against SARS-CoV-2 upon vaccination in seronegative individuals) after two vaccine doses.

Secondary objectives:

- To evaluate the safety and tolerability of the vaccine administered to the research subjects.

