3.2. Benefit-risk assessment

Despite side effects, the benefits of vaccines greatly outweigh the risks, as complications from COVID-19 can be very serious, especially in high-risk groups. For example, one study showed that one in three patients with chronic lymphocytic leukemia (CLL) who were hospitalized due to COVID-19 infection died (Mato A et al. 2020). A similar mortality risk has also been reported after stem cell transplantation (Ljungman P et al. 2020). Even healthy individuals without risk factors can experience severe complications from COVID-19. All individuals in Sweden, including those with immunosuppressive conditions, are recommended to be vaccinated against COVID-19 by the Public Health Agency of Sweden. Both the primary population with immunosuppression and control subjects would therefore have been offered vaccination within routine care, regardless of participation in the study.

For a large number of generally immunocompetent individuals, Comirnaty has not been shown to cause serious side effects (>30,000), except for anaphylactic reactions in a small number of individuals. We do not expect a higher safety risk in the primary population with immunosuppression in the study. Rather, the opposite may be true, that reactogenic reactions may be milder in the primary population.

A routine venous blood sample, where a small volume of blood (<50 ml) is taken, is standard practice in healthcare and does not involve any significant risks. The discomfort of the venipuncture is negligible. In routine healthcare and at each site, protective measures are in place to prevent research subjects from becoming infected with SARS-CoV-2 during their visits. In addition, clear information is provided to all visitors not to come to the hospital if they have COVID-19 symptoms. Face masks and visors will be used during patient contact.

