5.9.7. Discontinuation criteria

Participants may choose to withdraw from the study at any time without giving a reason. Specific grounds for **discontinuation of study treatment**

- The participant withdraws their consent
- Participants who do not meet the compliance requirements
- If SUSAR, SAE, severe AE, or other medical condition arises, where continued study participation could pose a risk to the participant, in the investigator's judgment, the study drug treatment will be discontinued. The participant will then be offered medical follow-up within the framework of the study.
- Participants who become pregnant during the study
- Severe/systemic allergic reaction to the vaccine.
- The patient has not completed follow-up (lost to follow-up).
- The investigator has the right to discontinue participation in the study if there are reasons that may affect the individual's safety.
- The relevant authority may terminate the study

If an individual withdraws, information collected during the time they were participating in the study will be used to perform the analyses described. A follow-up visit will be offered to individuals who have discontinued their participation.

No Data and Safety Monitoring Committee (DSMC) is planned to be established in this open-label, non-randomized study. This is because Comirnaty has already been studied in approximately 21,000 individuals regarding its safety profile. This is an open-label study, and we do not expect an increased number of AE/SAE/SUSAR in primary populations.

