6. STATISTICS

6.1. Determination of the number of subjects

The primary purpose of this study is to study the immune response after the mRNA vaccine Comirnaty in a small study population (Phase IV study) in a descriptive or exploratory manner. The number of research subjects in the patient groups is based on the number of available patients who could be included at the respective clinics and the feasibility at a time when vaccination has already begun in Sweden. Several of these diseases/conditions are rare, with Karolinska University Hospital having the largest cohorts in Sweden, but with a limited number of patients available to participate in clinical trials.

The primary evaluation variable is the effect measured as the proportion of individuals who seroconvert in patients versus controls. For this, odds ratios and

analyzed using the Chi2 test where $\alpha=0.05$. With a patient group size of N=540, the power is >80% even with a conservatively estimated effect size of 0.15.

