6.3.3. Analyses of secondary endpoints

- Proportion (95% CI) seroconverting to a positive response to SARS-CoV-2 IgG serology after two doses of vaccine, at 3 months and 6 months after the second vaccine dose, measured in the "two-dose vaccine population" compared with the control group.
- Proportion (95% CI) experiencing adverse events, with AE/SAE/SUSAR. Number and proportion (95% CI) experiencing local reactions and systemic reactions are measured in the "Full analysis set population".
- Proportion (95% CI) receiving a new diagnosis of SARS-CoV-2 infection through a positive PCR test is measured in the "Full analysis set population."

- Comparisons are made with the control group.

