6.4. Statistical methods

Continuous variables will be presented with mean and standard deviation [SD] for normally distributed values, and median and interquartile range (IQR) for non-normally distributed values. Categorical variables will be presented as frequency distributions.

Comparisons between patient groups and the control group will be made using the Chi-square test. P-values will be adjusted for multiple comparisons where necessary.

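### For adverse events and vaccine reactions the only between-group result specified is a chi-square p-value, which at 90 versus 90 cannot show which excesses of harm are ruled out

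*Combined protocol and SAP*

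**What the plan says.** The Synopsis background poses the safety question as a comparison: "It is also unclear at present whether they react differently than healthy individuals in terms of side effects". Safety and tolerability is the first secondary objective (4.1).

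For AE/SAE/SUSAR and for local and systemic reactions, section 6.3.3 plans proportions with 95% CIs in the full analysis set and adds: "Comparisons are made with the control group". It names no measure for that comparison. Section 6.4 gives the method: "Comparisons between patient groups and the control group will be made using the Chi-square test. P-values will be adjusted for multiple comparisons where necessary". It does not say which endpoints are adjusted, by what method, or over which family of tests.

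The odds ratio in the Synopsis and section 6.1 belongs to seroconversion: "The primary evaluation variable is the effect measured as the proportion of individuals who seroconvert in patients versus controls". The only power statement, also in 6.1, concerns the same variable.

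On expected harm, section 3.2 says "We do not expect a higher safety risk in the primary population with immunosuppression in the study". Section 5.9.7, explaining why there is no safety monitoring committee, says "we do not expect an increased number of AE/SAE/SUSAR in primary populations".

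**The concern.** The question is whether patients react differently from healthy people, and the stated expectation is that they do not fare worse. For that question a p-value is a weak summary. It does not give the size of an excess, and when it is not significant it does not say how large an excess remains possible. Two separate within-group intervals do not supply this reliably either; the interval for the difference has to be computed.

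Groups of 90 are small for uncommon events. If a clinically relevant excess is often missed, a non-significant result can easily be taken as support for the expectation in 3.2 and 5.9.7. Adjusting safety p-values, which 6.4 leaves open, would make this more likely, because it makes an excess of harm harder to detect.

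**Working it through.** **The plan's own figure.** Section 6.1 states: "With a patient group size of N=540, the power is >80% even with a conservatively estimated effect size of 0.15". The scale of 0.15 is not defined. Read as Cohen's w on 1 df, the noncentrality is 540 × 0.15² = 12.15 and power is about 94%, so the claim reproduces. It covers seroconversion with all 540 participants, a total that includes the 90 controls. For one 90 versus 90 comparison at the same w, the noncentrality is 180 × 0.15² = 4.05 and power is 52%. No power figure is given for any harm.

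**Inputs for the safety check.**
- 90 per patient group, five groups, 90 controls (5.1.1).
- Alpha 0.05 (6.1).
- Test: Pearson chi-square (6.4), taken without continuity correction.
- If adjusted: Bonferroni over five groups, 0.05 / 5 = 0.01. This is my assumption.
- Event rates: assumptions. The documents give no assumed AE or SAE rate for either group. For reactions they give frequency bands (3.1, Table 1: injection-site pain, fatigue, headache, chills and fever each at 1 in 10 or more) and 1% for severe local pain (5.8.3).

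**Method.** For every pair of counts (x controls, y patients), compute χ² = (p₂ − p₁)² / [p(1 − p)(1/n₁ + 1/n₂)], where p₁ = x/n₁ (controls), p₂ = y/n₂ (patients) and p is the pooled proportion. The miss rate is 1 minus the total binomial probability of the pairs in which χ² exceeds the critical value and patients have the higher rate.

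| Controls vs patients | Missed, 90 vs 90, alpha 0.05 | Missed, 90 vs 90, alpha 0.01 | Missed, 90 controls vs 450 pooled, alpha 0.05 |
|---|---|---|---|
| 1% vs 5% | 66% | 92% | 62% |
| 2% vs 6% | 75% | 92% | 70% |
| 5% vs 10% | 76% | 91% | 70% |
| 10% vs 20% | 53% | 77% | 36% |
| 50% vs 65% | 47% | 71% | 24% |
| 5% vs 15% | 37% | 63% | 20% |
| 50% vs 70% | 21% | 43% | 5% |
| 20% vs 40% | 16% | 35% | 3% |
| 5% vs 20% | 11% | 29% | 2% |

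**What an interval adds.** Illustrative counts, 90 per group, controls first, Newcombe 95% CI for the difference:

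| Events | Risk difference (95% CI), points | Unadjusted p | p × 5 |
|---|---|---|---|
| 1 vs 3 | +2.2 (−3.2 to 8.3) | 0.31 | 1.0 |
| 5 vs 10 | +5.6 (−2.9 to 14.3) | 0.18 | 0.89 |
| 9 vs 18 | +10.0 (−0.5 to 20.5) | 0.06 | 0.30 |

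All three are non-significant, yet the intervals leave open excesses of about 8, 14 and 20 points. The p-value shows none of this.

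**Sparse cells.** With 1/90 versus 7/90 the expected event count is (1 + 7) / 2 = 4 per group. Pearson gives p = 0.030 and Fisher's exact test p = 0.064, so the choice of test decides significance. With 0/90 events the exact two-sided 95% upper limit is 1 − 0.025^(1/90) = 4.0%.

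**The case against.** The strongest reply is that results are not reduced to a p-value. Section 6.3.3 plans proportions with 95% CIs in both populations, so a reader will see both rates and can subtract them. Section 6.1 calls the study descriptive or exploratory, and safety is secondary. The expectations in 3.2 and 5.9.7 are background rationale, not hypotheses to be confirmed. Ongoing safety oversight does not depend on the final tables: there is 24-hour SAE reporting, SUSAR reporting, annual safety reports and a steering committee that advises on stopping. A risk difference also adds no information beyond what 90 per group can carry.

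Most of this is fair, and it limits the point to reporting and interpretation. What remains is that the point difference follows from two proportions by eye but its uncertainty does not, and the plan specifies no other between-group result. An interval does not make the groups larger; it makes their limits visible.

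Three stronger readings are tempting and not supported:
- A reader might infer that safety p-values will be multiplicity-adjusted. Section 6.4 makes adjustment conditional and names no endpoint. The alpha 0.01 column shows what would follow if it were applied.
- A reader might infer that any real excess would usually be non-significant. The table contradicts this for larger excesses, especially with all patients pooled.
- A reader might infer that the plan treats non-significance as proof of safety. It says so nowhere.

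**Conclusion.** The point holds as a cheap improvement to the analysis plan. For AE/SAE/SUSAR and reactions, a chi-square p-value is the only between-group result specified, and whether it is adjusted is left open. At 90 versus 90 without adjustment, uncommon or moderate excesses are missed about half the time or more (53–76% for the four scenarios from 1% vs 5% to 10% vs 20%). Bonferroni over five groups, if applied, would make that 77–92%. Larger excesses are mostly detected: 5% versus 15% is missed in 37% and 20% versus 40% in 16%, or 20% and 3% with all patients pooled.

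These figures rest on assumed event rates, full planned recruitment and the uncorrected Pearson test. The textual finding, that no between-group estimate or interval is planned for harm, rests on none of them. Reading non-significance as absence of harm is a risk of interpretation, not a rule in the plan.

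**What to change.** In 6.3.3 and 6.4:

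1. For each patient group, and for all patients pooled, report the risk difference versus controls with an unadjusted 95% CI (Newcombe or Miettinen–Nurminen) for any AE, any SAE, local reactions and systemic reactions. Optionally repeat this by the severity grades already collected under 5.8.3.
2. Use exact limits for zero-event cells, and an exact test where expected counts are below 5.
3. Limit multiplicity adjustment to the seroconversion comparisons, and say so.
4. State that a non-significant safety p-value is not evidence of no increased risk.

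The cost is some wording and a few table columns, with no new data or participants. The downsides are that safety statements become more cautious, because the intervals are wide, and that unadjusted intervals will produce a few more chance signals.

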7 QUALITY CONTROL AND QUALITY ASSURANCE

7.1 Quality assurance and sponsor monitoring

It is the sponsor's responsibility to oversee the quality of the study. This is done, among other things, by performing a risk analysis of the study as a whole.

The sponsor is responsible for the study's monitoring plan, which should be based on the identified risks. The sponsor is also responsible for following up on the risks during the course of the study.

It is the sponsor's responsibility to ensure that staff are trained in the study.

7.2 Monitoring

To ensure that the study is conducted according to the protocol, that data is collected, documented, and reported in accordance with ICH-GCP (Good Clinical Practice) and applicable ethical and regulatory requirements, the study will be monitored before, during, and after the study. Monitoring is performed according to the study's monitoring plan and aims to ensure that the rights, safety, and well-being of the research subjects are safeguarded and that the data in the CRF is complete, accurate, and consistent with the source data.

Monitoring for this study will be carried out with the help of KTA (Karolinska Trial Alliance) support. The appointed monitor has documented GCP knowledge. The monitor will continuously check that the study is being conducted in accordance with the approved study protocol and complies with ICH-GCP. The monitor will also check that data is collected in such a way that it can be verified with source data. The respective operations manager will grant the monitor access to the CRF, patient records, and other source data.

Deviations from protocols or regulations will be documented and handled in accordance with the monitoring plan.

7.3 Source data

Records will be kept in accordance with current practice and the Patient Data Act (SFS 2008:355). Patient participation in the study will be noted in the medical records. Patient data will be collected according to the protocol and recorded continuously in study-specific patient forms (CRF) in electronic format. The collected data originates from source documents at the clinic, such as lab reports.

7.4 Deviations or serious violations

Violations and deviations from trial protocols, GCP, and other regulations that significantly and directly affect, or are highly likely to affect, research subjects in Sweden or the scientific value of the trial must be reported immediately within 7 days (from knowledge) to LV. It is the sponsor's responsibility to assess the consequences of any deviations that have occurred and, accordingly, to decide whether LV should be informed.

Minor deviations that do not affect the integrity or safety of research subjects, or significantly affect the scientific value of the trial, shall be documented in the trial documentation by the principal investigator and the sponsor.

7.5 Inspection

Authorized representatives of the sponsor and competent authorities may conduct inspections at the trial site, including source data verification. The investigator shall ensure that all source documents are available for inspection. The purpose of an inspection is to systematically and independently review all study-related activities and documents to determine whether these activities were performed, recorded, analyzed, and reported correctly in accordance with the protocol, Good Clinical Practice (GCP), and applicable regulations.

8 ETHICS

8.1 Compliance with protocols, GCP, and regulations

The study will be conducted in accordance with the protocol, the Declaration of Helsinki, ICH-GCP (Good Clinical Practice), and the applicable national and international regulations relating to this clinical study. This is to ensure the safety and integrity of the research subjects as well as the quality of the data collected.

8.2 Ethical review of the study

The final study protocol for drug trials must, as part of the application for a clinical drug trial permit, be approved by both the Ethical Review Authority and the Swedish Medical Products Agency before the trial can be conducted. The final version of the informed consent form and other information provided to the research subjects must be approved or given a written positive opinion by the Ethical Review Authority. The Ethical Review Authority and the Swedish Medical Products Agency must be informed of any changes to the protocol in accordance with applicable requirements.

8.3 Procedure for obtaining informed consent

The principal investigator at each trial site shall ensure that the research subject is given full and adequate verbal and written information about the study, its purpose, any risks and benefits, and inclusion/exclusion criteria. Research subjects must also be informed that they are free to withdraw from the study at any time without having to give a reason. The research subject shall be given the opportunity to ask questions and be allowed time to consider the information provided. If the person chooses to participate, the research subject and the investigator shall sign the consent form. A copy of the research subject information and the signed consent form shall be given to the research subject. The research subject's signed and dated informed consent must be obtained before any study-specific activity is performed in the study. Each research subject participating in the study will be identified by a research subject number on a research subject identification list. The research subject consents to monitors and inspectors having access to their medical records and other source data. If new information becomes available during the study, the research subject has the right to reconsider whether he/she wishes to continue participating.

In this study, informed consent may be signed on paper forms or electronically with Bank ID. The study population also includes English-speaking research subjects. These subjects will be informed in English and will sign an English version of the informed consent form. Signed informed consent for participation in the two extension parts of the study will be obtained before sampling begins.

8.4 Data protection

If any part of the data processing is carried out by another organisation, within or outside the EU, appropriate agreements and/or other documentation will be drawn up to ensure that the processing is carried out in accordance with the provisions of the Data Protection Regulation and other relevant legislation before any data transfer takes place.

The content of the informed consent form complies with relevant privacy and data protection legislation. The research subject information and informed consent form will provide research subjects with complete information about how their study data will be collected, used, and disclosed. The research subject information and informed consent form will explain how study data will be stored to maintain confidentiality in accordance with national data legislation.

All data processed by the sponsor will be pseudonymized and identified only by study code.

The informed consent form will also explain that for data verification purposes, authorized representatives of the sponsor, as well as the relevant authority, may require access to parts of hospital or study records relevant to the study, including the research subject's medical history.

8.5 Insurance

Research subjects are insured through patient injury insurance and drug insurance.

